10.2.2 Definitions

10.2.2.1 Evaluable for toxicity: All patients will be evaluable for toxicity from the time of their first treatment with axitinib, nivolumab, or the combination of axitinib and nivolumab.

10.2.2.2 Evaluable for objective response: Only those patients who have measurable disease present at baseline, have received at least one cycle of therapy, and have had their disease re-evaluated will be considered evaluable for response. These patients will have their response classified according to the definitions stated below. (Note: Patients who exhibit objective disease progression prior to the end of Cycle 1 will also be considered evaluable.)

10.2.2.3 Evaluable non-target disease response: Patients who have lesions present at baseline that are evaluable but do not meet the definitions of measurable disease, have received at least one cycle of therapy, and have had their disease re-evaluated will be considered evaluable for non-target disease. The response assessment is based on the presence, absence, or unequivocal progression of the lesions.

10.2.3 Disease Parameters

10.2.3.1 Measurable disease: Measurable lesions are defined as those that can be accurately measured in at least one dimension (longest diameter to be recorded) as ≥ 20 mm by chest x-ray, as ≥ 10 mm with CT scan, or ≥ 10 mm with calipers by clinical exam. All tumor measurements must be recorded in millimeters (or decimal fractions of centimeters).

Note: Tumor lesions that are situated in a previously irradiated area might or might not be considered measurable in the event that such

lesions have progressed subsequent to such radiation.

10.2.3.2 **Malignant lymph nodes:** To be considered pathologically enlarged and measurable, a lymph node must be ≥ 15 mm in short axis when assessed by CT scan (CT scan slice thickness recommended to be no greater than 5 mm). At baseline and in follow-up, only the short axis will be measured and followed.

10.2.3.3 **Non-measurable disease:** All other lesions (or sites of disease), including small lesions (longest diameter < 10 mm or pathological lymph nodes with ≥ 10 to < 15 mm short axis), are considered non-measurable disease. Bone lesions, ascites, pleural/pericardial effusions, lymphangitis cutis/pulmonitis, inflammatory breast disease, and abdominal masses (not followed by CT or MRI), are considered as non-measurable.

Note: Cystic lesions that meet the criteria for radiographically defined simple cysts should not be considered as malignant lesions (neither measurable nor non-measurable) since they are, by definition, simple cysts.

'Cystic lesions' thought to represent cystic metastases can be considered as measurable lesions, if they meet the definition of measurability described above. However, if non-cystic lesions are present in the same patient, these are preferred for selection as target lesions.

10.2.3.4 **Target lesions:** All measurable lesions up to a maximum of 2 lesions per organ and 5 lesions in total, representative of all involved organs, should be identified as **target lesions** and recorded and measured at baseline. Target lesions should be selected on the basis of their size (lesions with the longest diameter), be representative of all involved organs, but in addition should be those that lend themselves to reproducible repeated measurements. It may be the case that, on occasion, the largest lesion does not lend itself to reproducible measurement in which circumstance the next largest lesion which can be measured reproducibly should be selected. A sum of the diameters (longest for non-nodal lesions, short axis for nodal lesions) for all target lesions will be calculated and reported as the baseline sum diameters. If lymph nodes are to be included in the sum, then only the short axis is added into the sum. The baseline sum diameters will be used as reference to further characterize any objective tumor regression in the measurable dimension of the disease.

10.2.3.5 **Non-target lesions:** All other lesions (or sites of disease) including any measurable lesions over and above the 5 target lesions should be identified as **non-target lesions** and should also be recorded at baseline. Measurements of these lesions are not required, but the presence, absence, or in rare cases unequivocal progression of each should be noted throughout follow-up.

10.2.4 **Methods for Evaluation of Measurable Disease**

All measurements should be taken and recorded in metric notation using a ruler or

calipers. All baseline evaluations should be performed as closely as possible to the beginning of treatment and never more than 4 weeks before the beginning of the treatment.

The same method of assessment and the same technique should be used to characterize each identified and reported lesion at baseline and during follow-up. Imaging-based evaluation is preferred to evaluation by clinical examination unless the lesion(s) being followed cannot be imaged but are assessable by clinical exam.

10.2.4.1 Clinical lesions: Clinical lesions will only be considered measurable when they are superficial (e.g., skin nodules and palpable lymph nodes) and ≥ 10 mm diameter as assessed using calipers (e.g., skin nodules). In the case of skin lesions, documentation by color photography, including a ruler to estimate the size of the lesion, is recommended.

10.2.4.2 Chest x-ray: Lesions on chest x-ray are acceptable as measurable lesions when they are clearly defined and surrounded by aerated lung. However, CT is preferable.

10.2.4.3 Conventional CT and MRI: This guideline has defined measurability of lesions on CT scan based on the assumption that CT slice thickness is 5 mm or less. If CT scans have slice thickness greater than 5 mm, the minimum size for a measurable lesion should be twice the slice thickness. MRI is also acceptable in certain situations (eg, for body scans).

Use of MRI remains a complex issue. MRI has excellent contrast, spatial, and temporal resolution; however, there are many image acquisition variables involved in MRI, which greatly impact image quality, lesion conspicuity, and measurement. Furthermore, the availability of MRI is variable globally. As with CT, if an MRI is performed, the technical specifications of the scanning sequences used should be optimized for the evaluation of the type and site of disease. Furthermore, as with CT, the modality used at follow-up should be the same as was used at baseline and the lesions should be measured/assessed on the same pulse sequence. It is beyond the scope of the RECIST guidelines to prescribe specific MRI pulse sequence parameters for all scanners, body parts, and diseases. Ideally, the same type of scanner should be used and the image acquisition protocol should be followed as closely as possible to prior scans. Body scans should be performed with breath-hold scanning techniques, if possible.

10.2.4.4 PET-CT: At present, the low dose or attenuation correction CT portion of a combined PET-CT is not always of optimal diagnostic CT quality for use with RECIST measurements. However, if the site can document that the CT performed as part of a PET-CT is of identical diagnostic quality to a diagnostic CT (with IV and oral contrast), then the CT portion of the PET-CT can be used for RECIST measurements and can be used interchangeably with conventional CT in accurately measuring cancer lesions over time. Note, however, that the PET portion of the CT

introduces additional data which may bias an investigator if it is not routinely or serially performed.

10.2.4.5 Ultrasound: Ultrasound is not useful in assessment of lesion size and should not be used as a method of measurement. Ultrasound examinations cannot be reproduced in their entirety for independent review at a later date and, because they are operator dependent, it cannot be guaranteed that the same technique and measurements will be taken from one assessment to the next. If new lesions are identified by ultrasound in the course of the study, confirmation by CT or MRI is advised. If there is concern about radiation exposure at CT, MRI may be used instead of CT in selected instances.

10.2.4.6 Endoscopy, Laparoscopy: The utilization of these techniques for objective tumor evaluation is not advised. However, such techniques may be useful to confirm complete pathological response when biopsies are obtained or to determine relapse in trials where recurrence following complete response (CR) or surgical resection is an endpoint.

10.2.4.7 Cytology, Histology: These techniques can be used to differentiate between partial responses (PR) and complete responses (CR) in rare cases (e.g., residual lesions in tumor types, such as germ cell tumors, where known residual benign tumors can remain).

The cytological confirmation of the neoplastic origin of any effusion that appears or worsens during treatment when the measurable tumor has met criteria for response or stable disease is mandatory to differentiate between response or stable disease (an effusion may be a side effect of the treatment) and progressive disease.

10.2.4.8 FDG-PET: While FDG-PET response assessments need additional study, it is sometimes reasonable to incorporate the use of FDG-PET scanning to complement CT scanning in assessment of progression (particularly possible 'new' disease). New lesions on the basis of FDG-PET imaging can be identified according to the following algorithm:

- a. Negative FDG-PET at baseline, with a positive FDG-PET at follow-up is a sign of PD based on a new lesion.
- b. No FDG-PET at baseline and a positive FDG-PET at follow-up: If the positive FDG-PET at follow-up corresponds to a new site of disease confirmed by CT, this is PD. If the positive FDG-PET at follow-up is not confirmed as a new site of disease on CT, additional follow-up CT scans are needed to determine if there is truly progression occurring at that site (if so, the date of PD will be the date of the initial abnormal FDG-PET scan). If the positive FDG-PET at follow-up corresponds to a pre-existing site of disease on CT that is not progressing on the basis of the anatomic images, this is not PD.

Note: A 'positive' FDG-PET scan lesion means one which is FDG avid with an uptake greater than twice that of the surrounding tissue on the

attenuation corrected image.

10.2.5 Response Criteria

10.2.5.1 Evaluation of Target Lesions

IMPORTANT: *All calculations of percentage change in total tumor burden to assess response or progression should fully exclude from consideration any malignant lesions that were surgically resected at any time prior to the latest response assessment.*

Complete Response (CR): Disappearance of all target lesions. Any pathological lymph nodes (whether target or non-target) must have reduction in short axis to < 10 mm.

Partial Response (PR): At least a 30% decrease in the sum of the diameters of target lesions, taking as reference the baseline sum diameters.

Progressive Disease (PD): At least a 20% increase in the sum of the diameters of target lesions, taking as reference the smallest sum on study (this includes the baseline sum if that is the smallest on study). In addition to the relative increase of 20%, the sum must also demonstrate an absolute increase of at least 5 mm. See [Section 10.2.1](#) for exceptions during the first 12 weeks.

At least a 40% increase in the sum of diameters of target lesions at any time during the study, taking as reference the smallest sum measured on study (this includes the baseline sum if that is the smallest on study).

Appearance of one or more new lesions is also considered progression. See [Section 10.2.1](#) for exceptions during the first 12 weeks.

For patients who achieve a CR, either due to protocol therapy or surgical resection of any remaining malignant lesions, occurrence of a new lesion ≥ 10 mm or the short axis of a lymph node increasing to ≥ 15 mm at any time is considered PD.

An initial response (any decrease in tumor size) followed by growth of at least 20% (relative to the nadir) at any time is considered PD.

Patients who are removed from protocol therapy for resection of lesions that are increasing in size (per [Section 13.1.8.2](#)) will be considered to have PD at the time of tumor resection.

Stable Disease (SD):

Neither sufficient shrinkage to qualify for PR nor sufficient increase to qualify for PD, taking as reference the smallest sum diameters while on study.

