8.0 CRITERIA FOR REMOVAL FROM PROTOCOL THERAPY AND OFF STUDY CRITERIA

8.1 Criteria for Removal from Protocol Therapy

- a) For Arms A and C, progressive disease of $\geq 40\%$ increase in total tumor burden from baseline or nadir at any time during protocol therapy (see [Section 10.2](#)) (see exception below).
- b) For Arms A and C, progressive disease of $\geq 20\%$ increase in total tumor burden from baseline or nadir that occurs > 12 weeks after start of protocol therapy, except if a patient met the criteria for pseudoprogression in the first 12 weeks and the total tumor burden has subsequently stabilized or decreased with no additional growth (see [Section 10.2](#)) (see exception below).
- c) For Arm B, progressive disease of $\geq 20\%$ increase from baseline or nadir in total tumor burden at any time during protocol therapy (see [Section 10.2](#)).
- d) Response followed by $\geq 20\%$ increase in total tumor burden from the nadir at any time during protocol therapy (see [Section 10.2.5.1](#)) (see exception below).
- e) Appearance of one or more new lesions or unequivocal progression of non-target lesions (see [Section 10.2.5.2](#)) and refer to [Section 10.2.1](#) for exceptions within the first 12 weeks of therapy (see exception below).
- f) Resection of any malignant lesion within the first 12 weeks of protocol therapy (see [Section 13.1.8.1](#)).
- g) Resection of any lesion that is increasing in size at any time while on protocol therapy (see [Section 13.1.8.2](#)).
- h) Completion of planned therapy.
- i) Unacceptable toxicity due to protocol therapy (see [Section 5.0](#)).
- j) Refusal of further protocol therapy by patient/parent/guardian.
- k) Physician determines it is in patient's best interest.
- l) Development of a second malignancy.
- m) Pregnancy.
- n) Repeat eligibility studies (if required) are outside the parameters required for eligibility (see [Section 3.2](#)).

Exception: Patients on Arm C who meet the protocol defined criteria of disease progression prior to Cycle 22 of therapy, may cross-over and receive the remainder of their protocol therapy per Arm A. For those patients who cross-over, the total protocol therapy received on AREN1721 is not to exceed 26 cycles or 2 years, whichever comes first.

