10.2 Response Criteria for Patients with Solid Tumors

Response and progression will be evaluated in this study using the new international criteria proposed by the revised Response Evaluation Criteria in Solid Tumors (RECIST) guideline (version 1.1), with the exceptions described in [Section 10.2.1](#) below to account for possible "pseudoprogression" during treatment with immunotherapy (iRECIST).⁶² The major change in iRECIST is the concept of allowing for the possibility of "pseudoprogression", which occurs when standard RECIST v1.1 progression (> 20% increase in tumor burden from baseline) during the first 12 weeks of treatment is followed at the next assessment by tumor shrinkage.⁶³ Consistent with iRECIST and this definition of pseudoprogression, in the current study, further progression above and beyond the usual 20% threshold will be required to meet the definition of progressive disease for any patient who has not yet completed 12 weeks of protocol therapy.

Following baseline evaluation and treatment initiation, patients should be re-evaluated for lesion response or progression after Cycles 2, 4, 6, 9, 12 and then every 4 cycles thereafter with additional imaging required (1) after every cycle following possible pseudoprogression until subsequent response is documented, and (2) at any time clinical progression is expected. During follow-up, repeat imaging evaluations should occur according to the schedule described in [Section 7.2](#). Confirmatory scans should also be obtained 6-8 weeks (not less than 4 weeks) following initial documentation of objective response.

At each imaging timepoint, the largest diameter (unidimensional measurement) of each target, non-target, or new lesion and the shortest diameter (axis) for each malignant lymph node should be recorded. Any lesions that were surgically resected since the last imaging assessment should be explicitly noted, along with the date and rationale for removal, and an indication of whether the lesion had been increasing in size at the time of surgical removal.

IMPORTANT NOTE: *All calculations of percentage change in total tumor burden to assess response or progression should fully exclude from consideration any malignant lesions that were surgically resected at any time prior to the most recent response assessment.*

10.2.1 Exceptions for Possible Delayed Response ('Pseudoprogression') – only applicable for patients on Arms A and C

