If at the Week 12 assessment the total tumor burden has not yet diminished to $< 20\%$ increase from baseline or nadir, a patient may stay on protocol therapy so long as tumor shrinkage/stabilization continues to occur. If at any point after Week 12 the total tumor burden increases *and* is $\geq 20\%$ from baseline or nadir, this will be defined as progressive disease and the patient must be removed from protocol therapy.

Patients whose best response in the first 12 weeks is pseudoprogression, but who subsequently come off protocol therapy prior to any further assessment, will be considered as having progressive disease. This will include patients who are removed from protocol therapy due to resection of tumor lesions that are increasing in size (see [Section 13.1.8.2](#)).

Note: An increase in tumor size of $\geq 40\%$ at any time will be considered true progression and will result in removal from protocol therapy.

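### Section 10.2 defines progression for PFS inconsistently: the 5 mm minimum is missing from some clauses, and early 20-39% growth can turn on toxicity or clinician judgement

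*Combined protocol and SAP*

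**What the plan says.** PFS takes its definition of progression from Section 10 (Sections 9.4 and 10.2.7). The relevant clauses are these.

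**Millimetre minimum**
- Section 10.2.5.1, main clause: PD is growth of at least 20% over the smallest sum on study, and "the sum must also demonstrate an absolute increase of at least 5 mm".
- Section 10.2.5.1, nadir clause: any decrease in size "followed by growth of at least 20% (relative to the nadir) at any time is considered PD". Section 8.1(d) repeats this for removal from therapy, as a 20% or greater "increase in total tumor burden from the nadir at any time during protocol therapy". Neither gives a millimetre figure.
- 40% clauses: Section 10.2.5.1 has "At least a 40% increase in the sum of diameters of target lesions at any time during the study"; the note closing Section 10.2.1 says that such growth "at any time will be considered true progression and will result in removal from protocol therapy"; Section 8.1(a) has a 40% or greater "increase in total tumor burden from baseline or nadir at any time during protocol therapy". None gives a millimetre figure.

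**Growth of 20-39% in the first 12 weeks (Arms A and C)**
- Section 10.2: growth beyond the usual 20% "will be required to meet the definition of progressive disease for any patient who has not yet completed 12 weeks of protocol therapy".
- Section 8.1(b): the 20% removal rule applies only more than 12 "weeks after start of protocol therapy, except if a patient met the criteria for pseudoprogression in the first 12 weeks" and the burden has since stabilised or fallen.
- Section 10.2.5.1: 20% is PD, with a pointer to Section 10.2.1 for early exceptions.
- Section 10.2.1: a patient with 20% to under 40% growth from baseline may stay on treatment only if four conditions all hold. The clinician sees no rapid progression or sees benefit; performance status has not fallen; the drug is tolerated without a DLT; and no urgent intervention would be delayed.
- Section 10.2.1 also counts as PD a patient with early pseudoprogression who leaves therapy before another assessment.

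**The concern.** A primary endpoint needs one rule that gives one answer from one set of measurements. Here the answer can depend on which clause is applied. In the second case it can also depend on whether the patient had a DLT, lost performance status, or was judged by the clinician to be progressing fast. A toxicity condition inside an efficacy endpoint is awkward when one arm adds a drug to the other.

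The first scheduled scan falls inside the 12-week window. In Arm C, protocol-defined progression also opens crossover to axitinib (Section 4.5.3). The final analysis rests on 22 events and the futility look on 11, so a few disputed calls could matter.

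**Working it through.** **The plan's own figure.** Inputs (Sections 9.1-9.3): HR 0.40, one-sided alpha 0.15, 22 events, futility stop at 11 events if the observed HR exceeds 1.00, 1:1 allocation. With the Freedman drift (1 − HR)/(1 + HR) = 0.6/1.4 = 0.4286, the mean of Z is √11 × 0.4286 = 1.42 at the look and √22 × 0.4286 = 2.01 at the end. With correlation √0.5 this gives 7.8% early futility and 81.0% efficacy; the plan states 8% and 80%. At HR 1.0, efficacy is 13.9% against a stated 14%. The power figures reproduce and are not at issue.

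**Part 1: the 5 mm minimum.** Once the sum is below baseline, the smallest sum is the nadir. The main clause then needs ≥20% over nadir and ≥5 mm, while the nadir clause needs only ≥20% over nadir. Every case that meets the main clause meets the nadir clause, so if any one clause suffices, the 5 mm condition changes nothing.

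For nadir s, the disputed region is 0.20 × s ≤ growth < 5 mm, which requires s < 5/0.20 = 25 mm.

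| Nadir sum (whole mm) | Disputed growth |
|---|---|
| 10 | 2, 3 or 4 mm |
| 11-15 | 3 or 4 mm |
| 16-20 | 4 mm |
| 21 or more | none |

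With decimals, a 24.5 mm nadir leaves a window from 4.9 to under 5.0 mm.

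Example: sums of 20, 19 and 23 mm. Over nadir, 23/19 − 1 = 21.1%, and 23 − 19 = 4 mm. This is PD by the nadir clause and not by the main clause.

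After any shrinkage the nadir clause already covers the 40% clause. The 40% clause adds cases only when baseline is the smallest sum, and then only below 5/0.40 = 12.5 mm.

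**Part 2: early growth.** Cycles last 4 weeks and the first scans follow Cycles 2 and 4, that is weeks 8 and 16. Week 8 is therefore the only routine scan before week 12. Take a patient with no earlier shrinkage who goes from 50 to 65 mm at week 8: 65/50 − 1 = 30.0%, and 15 mm.

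| Text applied | All 10.2.1 conditions met | DLT has occurred |
|---|---|---|
| 10.2, sentence covering every patient under 12 weeks | 20% alone is not enough | 20% alone is not enough |
| 8.1(a)/(b), removal | not met | not met |
| 10.2.5.1 with the 10.2.1 exception | not PD | PD |

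The two columns differ only in toxicity. The 10.2.1 conditions are written for staying on treatment, but the pointer in 10.2.5.1 makes them the exception to the PD definition.

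The 10.2.1 clause on leaving therapy does not settle the matter. End-of-treatment imaging is required (Sections 7.1 and 16.2.1), but the clause does not say whether that scan is the further assessment, and it gives no PD date. This is an ambiguity rather than a conflict.

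**Size.** The documents give no rate for early 20-39% growth or for failing a 10.2.1 condition. Purely as an illustration, assume 28/2 = 14 patients per arm, 10-30% with such growth at week 8, and 10-30% of those failing a condition. The range is 14 × 0.10 × 0.10 = 0.14 to 14 × 0.30 × 0.30 = 1.26 patients per arm.

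**The case against.** On part 1, a coherent reading removes the conflict. Sections 10.2 and 16.2.1 adopt RECIST 1.1 with only the exceptions in 10.2.1, and the nadir clause is not among them. Its purpose may be to switch off the 12-week allowance once a tumour has shrunk, which would explain why 8.1(d) stands beside 8.1(b). On that reading the 5 mm minimum carries over. The reading is plausible, but the text does not state it. The reach is also small: patients have unresectable or metastatic disease, with up to five target lesions summed.

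On part 2, Section 8.1 governs removal from therapy, so its support for a PFS rule is indirect. Section 10.2 itself refers to 10.2.1. Both points stand as limits, but neither reconciles the sentence covering every patient with a PD clause whose exception is conditional.

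A reader might infer more than the documents support:
- *That Section 10.2 sets the early threshold at 40%.* It asks for more than 20% and gives no figure. The 40% comes from 10.2.1, 10.2.5.1 and 8.1(a).
- *That the 30% DLT limit in Section 9.5, or 0.30 × 14 = 4.2 patients, bounds the number affected.* That limit covers the first cycle only. The 10.2.1 condition covers any DLT up to the assessment, so weeks 5 to 12 fall outside the limit.
- *That the rule favours one arm.* Section 2.2 cites Grade 3-4 events of 19% with nivolumab alone, and 73% and 60% when it was combined with other VEGFR inhibitors. These come from different trials and are not DLT rates. An imbalance is possible, but its size and direction are not given.

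**Conclusion.** The concern holds in limited form. Part 1 is an inconsistency on a literal reading, confined to nadir sums below 25 mm, or below 12.5 mm for the 40% clause when baseline is the smallest sum. Part 2 is a conflict for growth of 20-39% from baseline without prior shrinkage in the first 12 weeks, and it allows toxicity or judgement to decide a PFS event.

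The conclusion rests on the wording alone and assumes that meeting any one PD clause is enough. The number of patients and the direction by arm cannot be determined; the illustrative range depends wholly on assumed rates. Neither the 22 events nor the 80% power is challenged. This should be fixed, because the endpoint is primary and the repair is mainly wording.

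**What to change.** Amend the protocol before the 11-event futility look:

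1. Add the 5 mm minimum to every percentage-growth PD clause: the nadir and 40% clauses in 10.2.5.1, the 40% note and the after-week-12 rule in 10.2.1, and 8.1(a), (b) and (d).
2. State that for PFS in Arms A and C, growth from baseline in the first 12 weeks without prior shrinkage is PD at 40% and at least 5 mm, by measurement alone. Leave the new-lesion and non-target rules as written. State that the 10.2.1 clinical criteria govern only whether treatment continues.
3. Amend the sentence in 10.2 covering every patient under 12 weeks to except those with prior shrinkage, for whom 20% over nadir and at least 5 mm is PD at any time. Without this, the nadir clause would still contradict that sentence.
4. State that the end-of-treatment scan counts as the further assessment. Where no later scan exists, date the fallback PD at the scan that showed the growth.

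Under these rules neither example is PD: the first grows 4 mm, and the second would need 50 × 1.40 = 70 mm.

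Apply the rules to enrolled patients from recorded measurements, with two exceptions: Arm C patients who have already crossed over, and patients already called PD who have no later scans. In the first group a later date would rest on scans taken on axitinib, although Section 9.3 keeps post-crossover outcomes out of the primary analysis. In the second group, re-derivation could turn an event into a censored time. For both, keep the recorded PD date in the primary analysis, list the cases and report a sensitivity analysis.

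The cost is an amendment and a re-derivation of PFS status. No new scans are needed, since Section 10.2 already has diameters recorded at each imaging time. A few patients with small-volume disease or early growth would be called PD somewhat later.
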